8.1. Number of Participants

An estimated number of 20-25 patients affected by TAAD and undergoing open heart surgery are usually admitted in mid/high-volume aortic centres (1). Therefore, it is estimated that the registry will encompass more than 5000 patients in total. Locally, the number of patients admitted to Glenfield Hospital (University Hospitals of Leicester NHS Trust) fulfilling the inclusion criteria between 1 January 2010 and 31 December 2025 is (average) 15-20 per year.

8.2. Sample Size Calculation

The impact of total aortic arch repair compared to more limited aortic resection on the early and late outcomes will be one of the main topics of research from this registry. Therefore, in the light of the expected limited frequency of this surgical strategy, we performed a sample size analysis considering the extent of distal aortic resection. Despite the limitation of a pooled analysis which did not take in to account the cumulative incidences from competing risk analysis and the segment of repeat operation, Poon et al. (24) estimated a pooled hazard ratio on 0.73 (95%CI 0.56-1.18) of freedom from any late aortic reoperation for total arch replacement. Based on this hazard ratio, a sample size of 163 patients per study groups would be enough to reject the null hypothesis (alpha 0.05, power 0.80). Pan et al. (25) reported a freedom from distal reoperation after ascending aortic resection at 8 years of 95.3% which was not statistically different from that of hemiarch or total aortic arch repair (92.4%, p=0.22). For the sample size calculation of a non-inferiority trial, we assumed a freedom rate from distal aortic reoperation of 95% and we considered that a difference in the reoperation rate as large as 10% in favor of a total aortic arch repair still allow the less extensive repair to be non-inferior (delta=0.1, power 0.90, one-sided confidence 97.5%), the required sample size would be 100 patients per each group. We assume that about 5% of patients have undergone total arch repair in this collaborative registry and therefore a study population of 4000 patients would be enough to investigate the impact of total aortic arch repair in preventing late aortic reoperation in patients with acute TAAD.

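### The 163 patients per group for a hazard ratio of 0.73 is a count of reoperation events, so 4000 patients do not give 80% power for the superiority question

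*Protocol*

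**What the plan says.** Protocol section 8.2 names total arch repair against more limited resection as one of the registry's main topics and sizes the registry on it in three steps.

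- **Superiority.** It cites a pooled analysis that "estimated a pooled hazard ratio on 0.73 (95%CI 0.56-1.18) of freedom from any late aortic reoperation for total arch replacement", and concludes that "a sample size of 163 patients per study groups would be enough to reject the null hypothesis (alpha 0.05, power 0.80"). It gives no event probability, length of follow-up or censoring for this step, and does not say whether alpha is one- or two-sided.
- **Non-inferiority.** It cites a series with "freedom from distal reoperation after ascending aortic resection at 8 years of 95.3"%, "not statistically different from that of hemiarch or total aortic arch repair (92.4%, p=0.22"). It then says "we assumed a freedom rate from distal aortic reoperation of 95"%, and with "delta=0.1, power 0.90, one-sided confidence 97.5%), the required sample size would be 100 patients per each group".
- **Registry size.** It assumes about 5% of patients had total arch repair and concludes that "a study population of 4000 patients would be enough to investigate the impact of total aortic arch repair" in preventing late reoperation.

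Section 8.3 (Statistical Analysis) fixes one-to-one propensity matching. Elsewhere the expected registry is more than 5000 patients (section 8.1) or more than 10000 (sections 3 and 13.3).

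**The concern.** Power to detect a hazard ratio depends on the number of events, not the number of patients. A patient count therefore cannot follow from a hazard ratio, alpha and power alone. Section 8.2 nevertheless goes straight from 0.73 to patients, and its next sentences cite freedom from reoperation of 92.4% to 95.3%, which would leave few events in 326 people.

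Aortic reoperation is a primary outcome (sections 3 and 6.2), and section 13.3 expects the registry's size to lower the risk of type II error. If 163 per group stands as sufficient, a matched comparison of that size showing no difference could be taken as adequately powered when it is not.

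**Working it through.** **Inputs from section 8.2.** Hazard ratio (HR) 0.73; alpha 0.05; power 0.80; 5% total arch, so 4000 × 0.05 = 200. Distal reoperation risk at 8 years is 100 − 95.3 = 4.7% after ascending resection and 100 − 92.4 = 7.6% after hemiarch or total arch; the plan itself assumes 5%. One-to-one allocation comes from section 8.3.

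**Reproducing 163.** With two-sided alpha, (1.960 + 0.842)² = 7.849 and (ln 0.73)² = 0.0990.

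- Schoenfeld: 4 × 7.849 / 0.0990 = 317 events in total.
- Freedman: 7.849 × (1.73/0.27)² = 322.2, so 323 events in total.
- Exponential test without censoring, per group: [1.960 × √(2 × 0.865²) + 0.842 × √(1 + 0.73²)]² / 0.27² = 162.3, rounded up to **163**.

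The last matches exactly, and it assumes that every patient has the event. Two groups of 163 make 326. One-sided alpha gives 125 to 127 per group and does not reproduce the figure. Comparing two proportions, with the hazard ratio applied to survival, never needs fewer than 249 per group at any baseline risk. Reading 0.73 as a risk ratio gives about 163 only at a baseline risk near 57%.

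**Power actually delivered.** Let p be the risk in the limited-repair arm and 1 − (1 − p)^0.73 the risk in the total arch arm. Power = Φ(0.3147 × √(D × a(1 − a)) − 1.960), where D is events and a is the total arch share (0.5 matched, 0.05 unmatched). For example, at p = 5% the other arm has 3.68% and the mean is 4.34%. Then 326 × 0.0434 = 14.1 events, and Φ(0.3147 × √(14.1 × 0.25) − 1.960) = 8.6%.

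| Risk, limited repair | 163 per group: events, power | 200 matched pairs: events, power | All 4000 (5:95): events, power |
|---|---|---|---|
| 4.7% | 13.3, 8.3% | 16.3, 9.3% | 186, 15.3% |
| 5% | 14.1, 8.6% | 17.4, 9.6% | 197, 16.0% |
| 7.6% | 21.5, 10.9% | 26.4, 12.5% | 300, 22.0% |
| 20% (assumed) | 57.1, 22.0% | 70.1, 26.0% | 790, 48.7% |
| 30% (assumed) | 86.3, 30.9% | 105.8, 36.7% | 1186, 65.6% |

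**What 80% would take.** At 5:95 the requirement is 7.849 / (0.05 × 0.95 × 0.0990), about 1670 events, or 42% of 4000 patients reoperated. With 200 pairs it is 317 of 400, or 79%. At 1:1 the patients needed per group are about 3655 at a 5% risk, 2401 at 7.6%, 905 at 20% and 599 at 30%.

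**Expected registry of 10000 (500 total arch).**

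| Risk, limited repair | 500 pairs: power, minimum detectable HR | All patients: power, minimum detectable HR |
|---|---|---|
| 5% | 18%, 0.39 | 33%, 0.56 |
| 7.6% | 25%, 0.47 | 47%, 0.62 |
| 15% (assumed) | 44% | 75% |
| 20% (assumed) | 55% | 86% |

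Power is for HR 0.73. The minimum detectable HR is at 80% power, with the total arch risk recomputed for each HR.

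**Non-inferiority.** 2 × 0.05 × 0.95 × (1.960 + 1.282)² / 0.10² = 99.8, so 100 per group. This reproduces, and 200 total arch patients cover it.

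**The quoted interval.** On the log scale the lower arm is ln(0.73/0.56) = 0.265 and the upper arm is ln(1.18/0.73) = 0.480. A Wald-type interval would have equal arms. Holding 0.73 and 0.56 gives an upper limit of 0.73²/0.56 = 0.95. Holding 0.73 and 1.18 gives a lower limit of 0.73²/1.18 = 0.45. Holding both limits gives an estimate of √(0.56 × 1.18) = 0.81.

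**The case against.** Four points can be made for the plan.

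- **The size does not rest on the superiority step alone.** This stands. The non-inferiority calculation is correct on its own inputs and is met by 200 total arch patients. A reader might infer that the 4000-patient conclusion fails altogether, or that the registry has no other power justification. The document supports neither. But section 8.2 closes by asking whether total arch repair prevents late reoperation. That is a superiority question, which a 10-point margin around a 5% event rate does not answer.
- **The low rates belong to a different endpoint.** This also stands. The 4.7% to 7.6% is distal reoperation, while the hazard ratio concerns any late aortic reoperation and the primary outcome covers every aortic segment from the index stay onward. The protocol gives no rate for that wider event, so it would be wrong to present 5% to 7.6% as the plan's rate for this calculation. The assumed 20% and 30% rows allow for this, and 4000 patients still fall short.
- **The registry may be larger than 4000.** True. At 10000 patients and an assumed 20% risk, using everyone reaches 86%, though 500 matched pairs reach only 55%. That is an argument for reporting those figures; it does not validate 163 or 4000.
- **Size is set by existing records, and the primary objective is prediction.** Correct. The error changes no recruitment, which limits its consequences to what is claimed.

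It is also tempting to conclude from the interval that the true hazard ratio is 0.81. The document cannot show that: the slip may be in the estimate or in either limit.

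**Conclusion.** The superiority statement is wrong as written. The figure of 163 per group is half of a requirement of about 317 to 326 events and equals a patient count only if essentially every patient is reoperated. On the section's own distal rates, 163 per group has 8% to 11% power, not 80%. For the same question, 4000 patients give about 9% to 12.5% matched and 15% to 22% using all; at an assumed 20% to 30% risk, 26% to 37% and 49% to 66%. The claim that 4000 suffices holds for non-inferiority only.

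This rests on two-sided alpha (the reading that reproduces 163), proportional hazards, the cited risks applied to the limited-repair arm, every total arch patient finding a match, and 8-year risks applying to everyone. The last is generous. Surgery runs to the end of 2024 and follow-up stops at the end of 2025 (sections 7.5 and 12.5), so late entrants have about one year, and death as a competing event removes further reoperations.

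The printed hazard ratio and interval are not consistent with each other on the log scale. Which number is wrong cannot be told from the protocol.

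**What to change.** In section 8.2:

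1. State the superiority requirement in events: about 317 at 1:1, or about 1670 at a 5:95 split, for HR 0.73 at two-sided 0.05 and 80% power.
2. State an assumed cumulative incidence of any aortic reoperation, with follow-up, censoring and competing death, labelled as an assumption and given as a range.
3. Withdraw 163 patients per group, and confine the statement that 4000 is enough to the non-inferiority question.
4. Report achievable power or the minimum detectable hazard ratio for the expected registry, matched and unmatched, as in the 10000-patient table above.
5. Check the hazard ratio of 0.73 and its interval against the cited pooled analysis, and rerun item 1 if the estimate changes.

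The cost is protocol wording and a less favourable power statement. No extra patients or data are needed.

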8.3. Statistical Analysis

Statistical analyses will be conducted using Stata v. 15.1 (StataCorp LLC, Texas, USA) and SPSS v. 29.0 (IBM Corporation, Armonk, NY, USA) statistical softwares. Continuous variables and outcomes will be summarized as mean and standard deviation as well as median and interquartile range. Categorical variables and outcomes will be reported as counts and percentages. A p<0.05 will be set for statistical significance. Differences between the study groups will be evaluated using the Fisher's exact test, the Chi-square test, the linear-by-linear association test, the Mann-Whitney test and the Kruskal-Wallis test. The McNemar test and paired samples T-test will be used in case of

analysis of paired groups. Propensity score matching will be performed to balance treatment strategies for baseline differences. A propensity score will be estimated using a non-parsimonious multilevel mixed-effects logistic regression considering the cluster effect of the participating centers whose results may be affected by the referral pathway, surgical techniques and perioperative care. Multilevel mixed-effects logistic regression model will include all available baseline variables. One-to-one propensity score matching will be performed using a caliper width of 0.2 of the standard deviation of the estimated logit. Standardized differences <0.10 will be considered an acceptable imbalance between the matched cohorts. The estimated propensity score will be also included into regression models to adjust for multiple confounders or for analysis within its strata.

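### Section 8.2 gives 163 patients per group for HR 0.73 without an event probability; 163 is about the number of reoperations needed per group, so the stated 80% power is unsupported

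*Protocol*

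**What the plan says.** Protocol section 8.2 bases its sample size on the extent of distal aortic resection, which it calls one of the registry's main research topics. There are three steps.

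- **Superiority.** A cited pooled analysis "estimated a pooled hazard ratio on 0.73 (95%CI 0.56-1.18) of freedom from any late aortic reoperation for total arch replacement". From this the protocol concludes that "a sample size of 163 patients per study groups would be enough to reject the null hypothesis (alpha 0.05, power 0.80"). No reoperation rate, follow-up time or censoring is given for this step.
- **Non-inferiority.** A second cited study reported "a freedom from distal reoperation after ascending aortic resection at 8 years of 95.3"%, not significantly different from "hemiarch or total aortic arch repair (92.4%, p=0.22"). For its own calculation the protocol says "we assumed a freedom rate from distal aortic reoperation of 95"%. With a margin of 10 percentage points it arrives at 100 patients per group.
- **Conclusion.** Taking total arch repair to make up about 5% of cases, "a study population of 4000 patients would be enough to investigate the impact of total aortic arch repair in preventing late aortic reoperation".

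Section 8.3 (Statistical Analysis) adds "A p<0.05 will be set for statistical significance" and, for treatment comparisons, "One-to-one propensity score matching will be performed using a caliper width of 0.2" of the standard deviation of the logit. It also allows the propensity score to be used as a regression covariate or for stratification.

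**The concern.** The precision of a log hazard ratio is set by the number of events. A patient count follows only after dividing by the probability that a patient has the event, and the superiority step contains no such probability. The figure 163 is close to the number of reoperations needed in each group, while the same paragraph treats reoperation as uncommon.

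Reoperation on the aorta is one of the primary outcomes in the synopsis. The section on strengths says the registry's size should reduce type II errors, and section 13.1 expects conclusive results on surgical strategies. If the 80% power is not real, a non-significant comparison of total arch with more limited repair would carry far less information than section 8.2 implies.

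**Working it through.** **Inputs.** HR 0.73, alpha 0.05, power 0.80 and 163 per group come from section 8.2. Sidedness is not stated for this step; two-sided is taken and one-sided is also tried. Equal groups follow from the per-group wording and the one-to-one matching in section 8.3. Freedom from distal reoperation of 95.3%, 92.4% and 95% comes from section 8.2.

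**Step 1: reproduce 163.** ln 0.73 = −0.3147, with square 0.0990; (1.960 + 0.842)² = 7.849.

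- Schoenfeld: 4 × 7.849 / 0.0990 = 317 events in total, 158.5 per group.
- Freedman: 7.849 × (1.73 / 0.27)² = 322 events in total, 161 per group.

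The stated 163 lies within about 1 to 3% of these event counts. One-sided alpha gives 250 to 254 events, 125 to 127 per group, which does not match.

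**Step 2: read 163 as patients.** Two groups make 326 patients. The share that must be reoperated is 317/326 = 97% to 322/326 = 99%. With one-sided alpha it is 250/326 = 77% to 254/326 = 78%.

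**Step 3: power of 163 per group at a given reoperation rate.** Let S be freedom from reoperation in the less extensive arm, so that freedom in the total arch arm is S^0.73. Expected events are d = 163 × [(1 − S) + (1 − S^0.73)]. Power in the intended direction is Φ(√(d/4) × 0.3147 − 1.960), with two-sided alpha.

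| S | Basis for S | Events d | Power | Patients per group for 80% power (317 events) |
|---|---|---|---|---|
| 95.3% | distal figure, borrowed | 13.3 | 8.3% | 3,889 |
| 95% | distal figure, borrowed | 14.1 | 8.6% | 3,655 |
| 92.4% | distal figure, borrowed | 21.5 | 10.9% | 2,401 |
| 90% | assumption | 28.4 | 13.1% | 1,822 |
| 80% | assumption | 57.1 | 22.0% | 905 |
| 50% | assumption | 146.2 | 47.7% | 354 |

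**Step 4: what the 4000 figure provides.** 5% of 4000 is 200 total arch patients. On the borrowed distal rates:

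- One-to-one matched, 200 versus 200: about 16 to 26 events and 9 to 12% power.
- Unmatched, 200 versus 3800: 15 to 22% by the Schoenfeld formula with 5:95 allocation, or 13 to 18% when the variance is taken as the sum of the reciprocals of the two arms' expected events.

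At an assumed 80% freedom, 200 versus 3800 gives 49% and 39% by these two formulas.

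**Step 5: which step 4000 rests on.** At 5% total arch, the non-inferiority size needs 100 / 0.05 = 2000 patients and the superiority size needs 163 / 0.05 = 3260. Of the two, only the superiority figure calls for more than 2000. The non-inferiority figure of 100 per group reproduces and contains no such error.

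**The case against.** The strongest objection is that the documents do not supply the event rate needed to say what the power is. The hazard ratio concerns any late aortic reoperation, whereas 95.3%, 95% and 92.4% are freedom from distal reoperation, and the 92.4% belongs to a mixed hemiarch and total arch group rather than to a control arm. This stands. A reader might infer that the protocol's own figures prove a power near 10%. They do not, because that result needs a rate borrowed from another endpoint.

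A reader might also infer that the registry could hardly detect HR 0.73. That does not follow either. The synopsis anticipates more than 10000 patients. With 500 versus 9500 and an assumed 20% of the less extensive arm reoperated, power is 76 to 86% depending on the formula. On the distal rates the same comparison gives 25 to 47%.

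It is likewise an inference that 163 began as an event count. Neither standard formula gives exactly 163, and the protocol does not show its calculation.

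Finally, this is a retrospective registry of existing cases. The calculation sets no recruitment target or stopping rule, arch extent is one topic among several, and the non-inferiority calculation stands by itself. This limits the consequences but does not make the sentence correct. No plausible reoperation rate gives 163 patients per group 80% power: even with half of the less extensive arm reoperated it is about 48%.

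**Conclusion.** The superiority statement in section 8.2 is wrong as written. For HR 0.73 with 80% power, equal groups and two-sided alpha 0.05, the requirement is about 317 to 322 reoperations in total. Calling 163 per group a number of patients is valid only if about 97 to 99% of them are reoperated, or about 77% with one-sided alpha. This conclusion needs no outside event rate.

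The size of the shortfall does need one. It is about 8 to 11% power if the distal rates are borrowed for the less extensive arm, and about 13%, 22% and 48% at assumed freedom of 90%, 80% and 50%. These figures assume proportional hazards and ignore competing deaths and loss to follow-up, which would reduce the events further. The claim that 4000 patients suffice is therefore unsupported for superiority. It has not been shown that the full registry is inadequate.

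**What to change.** In section 8.2:

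1. Replace the 163 patients per group by about 317 to 322 reoperations in total (1:1, two-sided alpha 0.05, power 0.80).
2. State an assumed rate for any aortic reoperation, which is the endpoint of the hazard ratio, and the number of events expected from it.
3. Restate the resulting power, or the expected width of the confidence interval, as a range over that rate for the analyses actually planned: one-to-one matched (about 200 versus 200 at 4000 patients) and unmatched adjusted (200 versus 3800). The percentages worked out above from the distal rates should not be copied in as the study's power, because they belong to a different endpoint and, for the unmatched comparison, also depend on the formula.
4. Remove the statement that 4000 patients are enough for the superiority question unless the restated figure supports it. The non-inferiority size of 100 per group needs no change on this account.

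The cost is a rewording of section 8.2 and a less favourable stated power. No extra recruitment or data collection is involved.

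### Neither calculation in Protocol 8.2 supports the claim that 4000 patients suffice to study total arch repair in preventing late reoperation, and the non-inferiority margin is not carried into 8.3

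*Protocol*

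**What the plan says.** Protocol 8.2 (Sample Size Calculation) names total arch repair against more limited resection as one of the registry's main topics and makes two calculations.

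- **Superiority, any late aortic reoperation.** A cited pooled analysis "estimated a pooled hazard ratio on 0.73 (95%CI 0.56-1.18) of freedom from any late aortic reoperation for total arch replacement". From this, "a sample size of 163 patients per study groups would be enough to reject the null hypothesis (alpha 0.05, power 0.80").
- **Non-inferiority of the limited repair, distal reoperation.** "For the sample size calculation of a non-inferiority trial, we assumed a freedom rate from distal aortic reoperation of 95" per cent. The margin is worded as "a difference in the reoperation rate as large as 10% in favor of a total aortic arch repair still allow the less extensive repair" to count as non-inferior, with settings "delta=0.1, power 0.90, one-sided confidence 97.5" per cent; "the required sample size would be 100 patients per each group".

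It then assumes that about 5% of patients had total arch repair and concludes that "a study population of 4000 patients would be enough to investigate the impact of total aortic arch repair in preventing late aortic reoperation". It does not say which calculation this rests on.

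Protocol 8.3 (Statistical Analysis) sets the general rule: "A p<0.05 will be set for statistical significance. Differences between the study groups will be evaluated using the Fisher's exact test", followed by other tests of difference, paired tests, 1:1 propensity matching and regression. Non-inferiority, the 10-point margin and the one-sided bound do not appear there.

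**The concern.** The closing sentence of 8.2 is about prevention, which is a superiority question about total arch repair. The only calculation there with 90% power asks the reverse question: whether limited repair is not worse by more than 10 points. A sample size for that question says nothing about power to detect a benefit of total arch repair. The other calculation does address a difference, but its 163 per group is implausibly small for a hazard ratio of 0.73 when the only event rates quoted are about 5 to 8%.

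Aortic reoperation is a primary outcome in the Synopsis, and 13.1 promises conclusive results on surgical strategies. At these event rates a difference test will usually give p>0.05. Next to a printed power of 0.90, such a result is easily taken as evidence that the limited repair is as good, which an underpowered difference test cannot show.

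**Working it through.** **Inputs from Protocol 8.2:** freedom 95% in both groups, margin 0.10, one-sided 0.025, power 0.90; hazard ratio 0.73, alpha 0.05, power 0.80; cited 8-year freedom 95.3% (ascending resection) and 92.4% (hemiarch or total arch); 5% total arch among 4000. **From 8.3:** p<0.05 and 1:1 matching. **Assumed:** two-sided testing; a two-proportion comparison; independent groups.

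**1. The 100 per group reproduces as non-inferiority.**
n = (1.960 + 1.282)² × 2 × 0.95 × 0.05 / 0.10² = 99.8, so 100. The 90% therefore belongs to a confidence bound set against a 10-point margin when the true difference is zero.

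**2. The 163 per group looks like events.**
(1.960 + 0.842)² = 7.849.
- Schoenfeld: 4 × 7.849 / (ln 0.73)² = 317 events in total.
- Freedman: 7.849 × (1.73/0.27)² = 322 events in total.

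That is about 159 to 161 events per group. The plan's 2 × 163 = 326 patients would supply 317 to 322 events only if 97 to 99% of them were reoperated. At 5% risk in the limited group, the risk under hazard ratio 0.73 is 1 − 0.95^0.73 = 3.68%. Then 163 × (0.05 + 0.0368) gives about 14 events, and power is Φ(√14.1/2 × 0.3147 − 1.960), about 9%.

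**3. What 4000 patients provide.**
4000 × 0.05 = 200 total arch repairs. The non-inferiority figure alone would need 100/0.05 = 2000 patients and the superiority figure 163/0.05 = 3260. The stated 4000 exceeds both.

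**4. Power of a difference test, 1:1, two-sided 0.05.**
Power = Φ[(|p₁ − p₂| − 1.960·se₀)/se₁], where se₀ = √(2p̄(1 − p̄)/n) and se₁ = √((p₁q₁ + p₂q₂)/n).

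At n = 200:
- 5% v 3.68%: (0.01325 − 1.960 × 0.02037)/0.02036 = −1.31, power 9.5%.
- 4.7% v 7.6%: (0.0290 − 1.960 × 0.02403)/0.02398 = −0.75, power 22.5%.

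| Per group | 5% risk, HR 0.73 | 4.7% v 7.6% |
|---|---|---|
| 100 | 6.7% | 13.4% |
| 163 | 8.5% | 19.2% |
| 200 (4000 patients) | 9.5% | 22.5% |
| 250 (5000 patients, cf. 8.1) | 10.9% | 27.0% |
| 500 (10,000 patients, cf. Synopsis) | 17.6% | 47.9% |

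For 80% power, about 3710 per group are needed in the first scenario and 1077 in the second.

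**5. Sensitivity.**
- At 200 per group, power is about 80% for 5% v 13% and 92% for 5% v 15%.
- The protocol gives no risk for *any* late reoperation. If it is assumed to be 10 to 30%, hazard ratio 0.73 has power of about 15 to 37% at 200 per group (event-based).
- Unmatched, 200 v 3800, with 5% risk and hazard ratio 0.73: about 197 events and power of about 16%.

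**The case against.** The strongest reply is that 8.2 has its own superiority calculation. A reader might infer that the non-inferiority figure was used to justify the prevention sentence. The text does not show this: 4000 covers both figures, and the closing wording on late aortic reoperation is nearer to the endpoint of the hazard-ratio calculation than to distal reoperation. This stands, so the point is that 8.2 does not distinguish the two. It does not rescue the sentence, because the 163 figure fails on its own terms.

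Other stronger readings should also be resisted.

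- **A non-inferiority analysis is missing.** Its detail may sit in a statistical analysis plan that is not at hand, and 8.3 is a general methods list for a registry expected to yield 42 studies. What can be said is that 8.3 states a decision rule that does not match the one behind the 90%.
- **Power is as low as 5%.** With equal rates in both groups, 5% is merely alpha and not power for prevention.
- **23% is the power for prevention.** It comes from rates at which the more extensive group, a mix of hemiarch and total arch, did worse.
- **The protocol will read p>0.05 as non-inferiority.** No section says so; this is a risk and not a stated rule.

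It is also fair that 8.3 assigns no particular test to late reoperation, that the Synopsis lists Kaplan-Meier, and that cases in a retrospective registry are limited by what exists. The power figures are therefore conditional. For a true difference as large as the margin, 200 per group would be adequate.

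**Conclusion.** The point holds in limited form. The 100 per group is correct for non-inferiority of the limited repair, and 200 total arch patients exceed it. Neither that figure nor the 163 per group supports the statement that 4000 patients suffice to study prevention of late reoperation. That 163 is an event count is an inference from its closeness to 317 to 322 total events; the protocol does not show its derivation.

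On the protocol's own rates and hazard ratio, superiority power at 200 per group is about 10 to 23%, against a stated 80%, and about 18 to 48% at 500 per group. Only the lower end of each range is in the prevention direction. These figures assume a two-proportion test at two-sided 0.05 with every total arch patient matched 1:1. Higher event risks would raise them, and matching losses would lower them.

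**What to change.** **In 8.2:**
- Say which question each figure serves.
- Limit the statement of 100 per group at 90% power to non-inferiority of limited repair on distal reoperation.
- Replace the 163 per group and the closing sufficiency statement with one of two things: an event-based superiority size (about 317 to 322 events in total at 1:1 for hazard ratio 0.73, with the event risk assumed), or the difference detectable with the expected number of total arch patients (roughly 5% v 13% at 80% power with 200 per group).

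**In 8.3 (Statistical Analysis):**
- For the non-inferiority comparison, compare the one-sided 97.5% upper bound for limited minus total arch, in cumulative incidence of distal reoperation at a stated horizon, with the 10-point margin already given in 8.2.
- State that p>0.05 in a difference test will not be read as non-inferiority.

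**Cost:** wording changes in two sections and one confidence bound from data already planned for collection. The downside is a less favourable stated power for superiority.

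### The 10-point non-inferiority margin is twice the assumed 5% reoperation rate, so 100 per group, and with it 4000 patients, is called enough on a margin that full prevention of reoperation by total arch repair would not exceed

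*Protocol*

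**What the plan says.** All the relevant statements stand in Protocol section 8.2 (Sample Size Calculation).

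- Source rates: a cited study "reported a freedom from distal reoperation after ascending aortic resection at 8 years of 95.3" percent, which was "not statistically different from that of hemiarch or total aortic arch repair (92.4%, p=0.22"). As reoperation rates these are 4.7% and 7.6%.
- Planning rate: "we assumed a freedom rate from distal aortic reoperation of 95" percent. A single figure is given and no group is named.
- Margin: "a difference in the reoperation rate as large as 10% in favor of a total aortic arch repair still allow the less extensive repair" to count as non-inferior, with "delta=0.1, power 0.90, one-sided confidence 97.5" percent.
- Result: "the required sample size would be 100 patients per each group".
- Step to the registry: "We assume that about 5% of patients have undergone total arch repair in this collaborative registry", from which the section concludes that "a study population of 4000 patients would be enough to investigate the impact of total aortic arch repair" in preventing late aortic reoperation.

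No reason is given for 10 points, in section 8.2 or elsewhere in the protocol. Reoperation on the aorta is a primary outcome (Synopsis; section 6.2), and section 8.2 names total arch against limited repair as a main research topic of the registry.

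**The concern.** A non-inferiority margin should mark the largest loss that would still be acceptable. It therefore has to be smaller than the loss that would follow if the more extensive operation worked perfectly. Here the margin is 10 points and the assumed event rate is 5%. Limited repair cannot be more than 5 points worse than total arch repair if its own rate is the assumed 5%.

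A declaration of non-inferiority would then be compatible with total arch repair making no difference, and equally with total arch repair preventing every reoperation. Those are the two answers that a surgeon choosing the extent of repair needs to tell apart. The same margin also makes the required number small (100 per group), and that number helps to support the statement that 4000 patients are enough.

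**Working it through.** **Inputs (Protocol 8.2).** Reoperation rate p = 0.05 in both groups, margin 0.10, one-sided alpha 0.025 (z = 1.960), power 0.90 (z = 1.282), total arch share 5%. Section 8.3 plans one-to-one propensity matching.

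**1. The plan's own figure.** n per group = (1.960 + 1.282)² × 2 × 0.95 × 0.05 / 0.10² = 99.8, so 100. It reproduces, which confirms that delta is an absolute 10 points. A margin of 10% relative to the 5% rate (0.5 points) would need 39,929 per group.

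**2. Margin against event rate.** 10 / 5 = 2. With limited repair at 5% and total arch repair at 0%, the true difference is 5 points, half the margin. The highest rate cited in the section, 7.6%, is also below 10 points.

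**3. Probability of declaring non-inferiority.** P = Φ((0.10 − d)/SE − 1.96), where d is the true difference and SE = √(p₁(1−p₁)/n₁ + p₂(1−p₂)/n₂). For 5% against 0% at 200 per group, SE = √(0.0475/200) = 0.0154, so P = Φ(0.05/0.0154 − 1.96) = Φ(1.28) = 0.90.

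| True rates, limited vs total arch | 100 per group | 200 per group | 500 per group |
|---|---|---|---|
| 5% vs 0% | 63% | 90% | 99.9% |
| 7.6% vs 0% | 15% | 25% | 53% |
| 10% vs 5% | 27% | 48% | 85% |

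The 200 and 500 are 5% of 4000 and of 10,000 patients, matched one to one. Exact binomial probabilities for 5% against 0% are 62%, 87% and 99.5% with Wald limits, and 44%, 70% and 98.8% with Newcombe limits.

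**4. The other reading of the 5%.** If it is the total arch rate, the margin allows 5 + 10 = 15% with limited repair: three times the risk, or a hazard ratio of ln(0.85)/ln(0.95) = 3.2.

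**5. What tighter margins need.** n per group = 0.998/margin², with the other inputs unchanged; total = n/0.05.

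| Margin | Per group | Registry patients at 5% total arch |
|---|---|---|
| 5 points | 400 | 8,000 |
| 4.5 points | 493 | 9,860 |
| 4 points | 624 | 12,480 |

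These totals assume that every total arch patient is matched and has a known 8-year status.

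**6. What 4000 patients support.** Margin at 90% power = 3.2415 × √(0.0475 × (1/n₁ + 1/n₂)). This gives 7.1 points for 200 pairs and 5.1 points for 200 against 3800 unmatched. Neither is below 5 points.

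**7. Follow-up.** Surgery spans 2010 to 2024 and follow-up ends on 31 December 2025 (Synopsis). Only patients operated on by the end of 2017 could have 8 years of potential follow-up. With even accrual that is 8/15 of them, so about 107 of 200 or 267 of 500. For 267 pairs the supported margin is 6.1 points.

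**The case against.** **The calculation only supports feasibility.** Section 8.3 describes no non-inferiority test and section 6.2 states no such objective. The size of a margin is also partly a clinical judgement, since section 5.1 weighs the early risk of extensive repair against late complications. This stands in part and limits the practical weight of the point. It does not remove it: the protocol itself fixes the margin, gives no clinical argument for it, and draws a sufficiency statement from it.

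**A reader might infer that the test cannot fail, or that its result would carry no information.** The figures do not support that. At 10% against 5% it fails about half the time with 200 per group, and at 15% against 5% it passes only 2.5% of the time. At 100 per group it can also fail when total arch repair prevents everything. What always holds, with limited repair at 5%, is that the true difference lies inside the margin.

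**A reader might infer that the registry would conclude both that total arch repair reduces reoperation and that limited repair is non-inferior.** That is not supported either. The hazard ratio of 0.73 in section 8.2 corresponds to 5% against 3.7%, or 7.6% against 5.6%. Power to show superiority is then about 9 to 12% at 200 pairs, 17 to 25% at 500 pairs, and at most 47% for 500 against 9500 unmatched. That ratio also refers to any late aortic reoperation, not to distal reoperation.

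**A reader might infer that the registry already supports a margin of 3 to 4.5 points.** Under one-to-one matching, 4.5 points needs close to 10,000 patients with complete 8-year status, and 3 points needs 1,110 per group, or 22,200 patients.

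**Conclusion.** The point holds in this form. A 10-point margin set without justification against an assumed 5% rate cannot separate no cost of limited repair from full prevention of reoperation by total arch repair. With limited repair at 5% and total arch repair at 0%, non-inferiority would be declared in about 63%, 90% and 99.9% of cases at 100, 200 and 500 per group. If the 5% belongs to total arch repair, a threefold rate is tolerated. So the non-inferiority calculation does not show that 4000 patients are enough, and at that size no margin below 5 points is supported.

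This rests on reading delta as absolute, which the reproduced 100 confirms; on the normal approximation, with Newcombe limits giving lower probabilities; and on the 5% total arch share in section 8.2. The separate figure of 163 per group, based on the hazard ratio, is not assessed here.

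**What to change.** Delete the non-inferiority claim from section 8.2, together with its use in justifying 4000 patients. State instead that the difference in cumulative incidence of reoperation between total arch and limited repair will be estimated with death as a competing event and reported with its 95% confidence interval. Give the precision expected at the actual number of total arch patients and their follow-up. As a guide, at 5% in both groups the half-width is 1.96 × √(0.095/n): about 4.3 points for 200 pairs and 2.7 points for 500 pairs, before any loss from incomplete 8-year follow-up.

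If a non-inferiority claim is kept, name the group to which the 5% applies, justify a margin below that rate, and restate the size it needs from the table in the working, with an allowance for patients who cannot reach 8 years.

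The first option costs protocol wording only. The price of either is that non-inferiority becomes harder, or at 4000 patients impossible, to claim. A tighter margin may need more total arch patients than the registry holds.
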